3. Compare the mean number of procedures that required Conversion to Open using NIFC vs WLI alone.
4. Compare the mean Volume of Bleeding using NIFC vs WLI alone.
5. Compare the Incidence rate of Bile Leakage from the liver bed using NIFC vs WLI alone.
6. Compare the Incidence rate of Bile Duct Injury (BDI) using NIFC vs WLI alone.
7. Compare the mean Surgeon Confidence Level using NIFC vs WLI alone.

5. Study Endpoints

a. Primary Endpoint:

Detection Rate (DR) of each particular extra-hepatobiliary structure during Laparoscopic Cholecystectomy (LC) defined as the total number of patients in which the particular structure is detected before and after dissection in that arm of the Study (WLI or NIFC), divided by the total number of patients in that arm. Extra-hepatobiliary structures to be included in this assessment: Cystic Duct, Right Hepatic Duct, Common Hepatic Duct, Common Bile Duct, Cystic-CBD junction, Cystic-Gallbladder junction, and any Accessory Ducts.

b. Secondary Endpoints:

1. The DR for students/residents only (apart from experienced surgeons), both before and after dissection.
2. Time to Clip
3. Incidence of Conversion to Open Surgery
4. Volume of Bleeding
5. Incidence of Bile Leakage from the liver bed
6. The mean Incidence of Bile Duct Injury (BDI)
7. Surgeon Confidence Level

6. Covariates

Besides the comparison of the outcomes in both study arms, we will conduct an exploratory analysis to identify potential effect modifiers. The following baseline variables will be considered:

- 1) Patient data:
 - a) Age
 - b) Gender
 - c) BMI
- 2) Patient history/condition:
 - a) obesity
 - b) liver disease
 - c) lithiasis
 - d) surgery status (elective/urgent/emergent)
- 3) Intra-operative factors:
 - a) amount of fat covering cystic artery
 - b) amount of inflammation
 - c) presences of adhesions / scar tissue
- 4) Surgeon expertise (resident/attendant)

7. Additional Observations (NIFC group only)

a. “Reflux Maneuver”

According to previous publications, in some cases the Cystic Duct may not be seen with NIFC because the Cystic Duct may not contain ICG at the time of viewing. In those cases, a “reflux maneuver” [defined as using an atraumatic laparoscopic instrument to push on the Common Bile Duct in order to move more of the ICG from the Common Bile Duct through the Cystic Duct into the Gallbladder – thereby increasing visualization of the Cystic-Gallbladder junction] can be performed.

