<hr/> 
1. Length of hospital stay: _____ (days)
 
2. Was patient readmitted: No  Yes  If Yes, complete the following:
 
Days after discharge: _____ (NOTE: Day of Surgery is Day "0")Reason for readmission: _____Treatment administered: _____Length of stay: _____ (days) 
3. Death (30 d): No  Yes  If Yes, cause of death: _____
 
4. Complications: No  If No, you have completed this form. Yes  If Yes, please continue...
 
Indocyanine green drug reactions: No  If No, skip to surgical complications. Yes  If Yes, continue
Flushing? No  Yes  If yes, please complete:
Treatment required? No  Yes If Yes, what treatment: _____Urticaria? No  Yes  If yes, please complete:
Treatment required? No  Yes If Yes, what treatment: _____Other possible drug reaction? No  Yes  If Yes, please complete:
Describe: _____Onset (day of surgery is "0"): _____Duration (Hours): _____Treatment required? No  Yes If Yes, what treatment: _____ <hr/> 
MULTICENTER TRIAL
 
Page 1 of 2
 
POSTOP-CRF v1.0
		

Near Infrared Incisionless Fluorescent Cholangiography (NIFC)

2

POST-OPERATIVE FORM

b. Hemorrhage? No Yes If Yes, please complete:

- i. ... requiring transfusion? No Yes
- ii. ... requiring re-operation? No Yes
- iii. ... requiring longer hospitalization? No Yes

c. Intra-abdominal pain in right upper quadrant? No Yes

d. Bile leak (without bile duct injury)? No Yes If Yes, please complete:

- i. ... requiring percutaneous drainage? No Yes
- ii. ... requiring reoperation? No Yes
- iii. ... treated with percutaneous drainage only? No Yes
- iv. ... treated with transpapillary stent? No Yes
- v. ... treated with percutaneous drainage and transpapillary stent? No Yes

vi. Source of leak:

1. cystic duct stump leak? No Yes
2. liver bed? No Yes
3. never determined? No Yes

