e. Bile duct injury? No Yes If Yes, complete separate BDI form

g. Bile Duct Injury (BDI) Form

Near Infrared Incisionless Fluorescent Cholangiography (NIFC)

BILE DUCT INJURY FORM

INSTITUTION: _____ PATIENT ID: _____ PROCEDURE DATE: _____

FORM COMPLETED BY: _____ FORM COMPLETION DATE: _____
(PRINT)

1. How was the injury recognized? Intraoperatively. Go to #2 Postoperatively. Go to #3

2. Intraoperative information:

a. Bile leak? No Yes If Yes, where?

- i. Cystic duct
- ii. Common bile duct
- iii. Common hepatic duct
- iv. Right hepatic duct
- v. Left hepatic duct
- vi. Small accessory duct
- vii. Liver bed
- viii. Couldn't tell
- ix. Other. Please specify: _____

b. Could the cut end of the tubular structure be seen? No Yes

c. Partial or complete occlusion? No Yes If Yes, what was the mechanism caused the occlusion?

- i. Tie or clip at cystic common duct junction
- ii. Scissor
- iii. Cautery
- iv. Ultrasonic dissector
- v. Other. Please specify: _____

3. Postoperative information:

a. Recognized postoperative day: _____ (day of operation is Day "0")

b. Diagnosed or suspected by imaging? No If No, skip to #c Yes If Yes,

- i. MRCP
- ii. CT scan
- iii. Ultrasound
- iv. Hida scan

MULTICENTER TRIAL

Page 1 of 3

BDI-CRF v1.0

Near Infrared Incisionless Fluorescent Cholangiography (NIFC)

BILE DUCT INJURY FORM

c. ERCP attempted/Performed? No If No, skip to #d Yes If Yes,
i. Unsuccessful
ii. Injury identified
iii. Injury stented
iv. CBD stone in addition
v. Other. Please specify: _____

d. Percutaneous transhepatic intervention performed? No If No, skip to next question Yes If Yes,
i. Drainage of duct(s) only
ii. Stent of duct(s)
iii. Other. Please describe: _____

[figure not shown]
e. Percutaneous subhepatic drainage? No If No, skip to next question Yes If Yes,
i. By CT scan
ii. By ultrasound

4. Re-operation for injury? No If No, skip to next question Yes If Yes,
a. Date of first reoperation: _____
b. Number of days postoperative: _____ (Original lap chole surgery date is Day "0")
c. Drain only? No Yes
d. Roux-en-y reconstruction? No Yes
e. T-tube placement? No Yes
f. End-to-end repair? No Yes
g. Other? No Yes If yes, please specify: _____
h. Additional surgeries to treat bile duct injury? No Yes If yes, answer #a-g above, with the date of each reoperation on additional forms as needed.

Near Infrared Incisionless Fluorescent Cholangiography (NIFC)

BILE DUCT INJURY FORM

5. Classification of bile duct injury (per Strasberg-Bismuth):

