[figure not shown]

- Type A: Cystic Duct leak or leak from small ducts in the liver bed
- Type B: Occlusion of a part of the biliary tree, usually an aberrant right hepatic duct
- Type C: Transection without ligation of an aberrant right hepatic duct
- Type D: Lateral injury to major bile duct
- Type E1: Transection >2cm from confluence
- Type E2: Transection <2cm from confluence
- Type E3: Transection in hilum
- Type E4: Separation of major ducts in hilum
- Type E5: Type C plus injury in hilum

6. Please attach to this form all operative reports, procedure reports, imaging and pathology reports from the original laparoscopic cholecystectomy to the most recent operation. Thank you.

h. Schedule of events

(from **Section 8.f. Trial Flow**)

i. WMA Declaration of Helsinki - Ethical Principles for Medical Research Involving Human Subjects

Adopted by the 18th WMA General Assembly, Helsinki, Finland, June 1964 and amended by the:

- 29th WMA General Assembly, Tokyo, Japan, October 1975
- 35th WMA General Assembly, Venice, Italy, October 1983
- 41st WMA General Assembly, Hong Kong, September 1989
- 48th WMA General Assembly, Somerset West, Republic of South Africa, October 1996
- 52nd WMA General Assembly, Edinburgh, Scotland, October 2000
- 53rd WMA General Assembly, Washington DC, USA, October 2002 (Note of Clarification added)
- 55th WMA General Assembly, Tokyo, Japan, October 2004 (Note of Clarification added)
- 59th WMA General Assembly, Seoul, Republic of Korea, October 2008
- 64th WMA General Assembly, Fortaleza, Brazil, October 2013

i. Preamble

1. The World Medical Association (WMA) has developed the Declaration of Helsinki as a statement of ethical Principles for medical research involving human subjects, including research on identifiable human material and data.

The Declaration is intended to be read as a whole and each of its constituent paragraphs should be applied with consideration of all other relevant paragraphs.

2. Consistent with the mandate of the WMA, the Declaration is addressed primarily to physicians. The WMA encourages others who are involved in medical research involving human subjects to adopt these Principles.

ii. General Principles

3. The Declaration of Geneva of the WMA binds the physician with the words, "The health of my patient will be my first consideration," and the International Code of Medical Ethics declares that, "A physician shall act in the patient's best interest when providing medical care."

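### Bile duct injury is undefined, and two case report forms classify the same leaks in opposite ways, so the counts for secondary endpoints 5 and 6 depend on how each site answers

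*Combined protocol and SAP*

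**What the plan says.** Section 5.b makes endpoint 5 "Incidence of Bile Leakage from the liver bed" and endpoint 6 the incidence of BDI. Neither is defined further. Section 13.a calls injury the main secondary outcome.

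Three forms collect the data:

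- **Post-operative form (Appendix f), item 4.** One question reads "d. Bile leak (without bile duct injury)? No Yes If Yes, please complete". Its source list includes "1. cystic duct stump leak? No Yes" and "2. liver bed? No Yes", plus a never-determined option. Item 4.e then asks separately about bile duct injury, and only a Yes leads to the BDI form.
- **BDI form (Appendix g), item 5.** Under "5. Classification of bile duct injury (per Strasberg-Bismuth" the first category is "Type A: Cystic Duct leak or leak from small ducts in the liver bed".
- **Intra-operative surgeon form (Appendix d).** Item 6 records bile leakage as liver bed or other (free text). Item 11 asks whether a BDI occurred and, if so, sends the surgeon to the BDI form. It gives no definition.

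Section 12.e asks for the BDI form whenever the procedure results in a bile duct injury, again without a definition.

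**The concern.** The two forms do more than leave a detail open. They give opposite answers for the same event: a cystic-stump or liver-bed leak is not an injury on one and is a Type A injury on the other. The BDI form is reached only after someone has already answered Yes to an undefined injury question. A site that treats item 4.d as the final place for a leak never sees the Type A category, while a site used to the Strasberg-Bismuth scheme may answer Yes to 4.e. Both would be following the protocol.

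At stake is what the injury count means. With so few events expected, the trial can contribute little beyond a descriptive count and ratio for injury, and those depend on the case definition.

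**Working it through.** **1. Where each leak can be counted**

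| Leak source | Site treats it as a leak without BDI | Site treats it as Type A BDI |
|---|---|---|
| Liver bed | Endpoint 5 only | Endpoints 5 and 6 |
| Cystic duct stump | Neither (endpoint 5 is limited to the liver bed) | Endpoint 6 |

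No section says which column applies, bars counting in both endpoints, or provides for adjudication. Nothing stops a site answering Yes to both 4.d and 4.e, although that contradicts the wording of 4.d.

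**2. The plan's own figure**

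Inputs from section 13.a: 8/1000 (control), 2/1000 (NIFC), 500 per arm, stated power 15%. Section 13.b plans Fisher's exact or chi-square for BDI. No sidedness is given for BDI; the one-sided 5% level in section 13.a is stated for the detection-rate table.

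Normal approximation with continuity correction, two-sided 5%:

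- Pooled rate = (0.008 + 0.002)/2 = 0.005
- SE under the null = √(2 × 0.005 × 0.995/500) = 0.00446
- SE under the alternative = √[(0.008 × 0.992 + 0.002 × 0.998)/500] = 0.00446
- Power = Φ[(0.006 − 1/500 − 1.96 × 0.00446)/0.00446] = Φ(−1.06) = 14.4%

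This agrees with 15% to within a point. Exact Fisher power is 18.1% one-sided and 9.9% two-sided. The contradiction between the forms does not depend on any of these figures.

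**3. Expected injuries at the planning rates**

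- Control: 500 × 0.008 = 4
- NIFC: 500 × 0.002 = 1
- Ratio: 1/4 = 0.25

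Moving one leak in each arm into BDI gives 5 versus 2, ratio 0.40.

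**4. Illustration: Type A counted at every site**

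Two assumptions are needed because the documents are silent: the planning rates exclude Type A, and Type A occurs at the same rate x in both arms. Expected counts are 500 × (0.008 + x) and 500 × (0.002 + x).

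| Assumed x | Control vs NIFC | Ratio | Power, two-sided corrected | Power, one-sided Fisher |
|---|---|---|---|---|
| 0 | 4 vs 1 | 0.25 | 14.4% | 18.1% |
| 0.5% | 6.5 vs 3.5 | 0.54 | 9.3% | 14.6% |
| 1% | 9 vs 6 | 0.67 | 7.5% | 13.0% |
| 2% | 14 vs 11 | 0.79 | 6.0% | 10.6% |

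At x = 0.5% the added events (2.5 + 2.5 = 5) equal the planned ones (4 + 1 = 5); above that they outnumber them. The table describes uniform inclusion. Mixed coding across sites, with the same Type A rate in both arms, would fall between the first row and the row for the true x.

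**The case against.** Several points on the other side stand.

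- **A reader might infer that the forms bias the comparison between arms.** The documents do not show this. Randomisation is 1:1 within site (section 8.d), so a site's coding habit affects both arms alike. Surgeons are not blinded (also 8.d) and complete item 11 themselves, so coding that differs by arm cannot be excluded, but nothing in the plan demonstrates it.
- **A reader might infer that the analysis cannot repair the problem.** For endpoint 6 it largely can. If BDI is restricted to Types B to E, a Type A record drops out at one site, a 4.d leak was never in at another, and the two agree. No such restriction is planned, however, and it does not secure endpoint 5. A site that codes a post-operative leak as BDI may answer No to 4.d and skip its source fields. Type A merges stump and liver bed. Item 3 of the BDI form, for injuries recognised after surgery, has no leak-source field, although item 2.a has one for injuries recognised during surgery. The source would then have to be found in the reports attached under item 6.
- **Overlap is not in itself an error.** The plan does not call endpoints 5 and 6 mutually exclusive. The fault is that the rule is missing and the forms disagree.
- **Loss of power changes no decision.** Section 13.a already concedes that power for injury is inadequate.
- **The planning rates may already include Type A.** The documents do not say. If they do, adding x on top counts those leaks twice, and a Types B to E definition would leave fewer than 4 versus 1 expected events.

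**Conclusion.** The contradiction between the post-operative and BDI forms is plain on their face, and nothing elsewhere in the protocol resolves it. Followed as written, the forms can give different injury counts for identical patients, and can leave the liver-bed source of a post-operative leak unrecorded.

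The size is uncertain. What is firm is that the planning rates imply 4 versus 1 injuries, so a handful of leaks alters the count and the ratio. The range of 6.5 versus 3.5 to 14 versus 11 (ratio 0.54 to 0.79) rests on an assumed Type A rate of 0.5% to 2%, equal in both arms, counted at every site, and not already within 8/1000 and 2/1000. It shows how far the ratio could be diluted. It does not measure inconsistent coding or bias between arms. The point concerns the main secondary outcome and leaves the primary detection-rate comparison untouched. It should be settled before enrolment, because coding choices are hard to reconstruct afterwards.

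**What to change.** State one rule in section 5.b on whether Type A counts in endpoint 6, and apply the same rule in section 13.b. One workable version defines BDI as Types B to E and counts Type A once, as bile leak, by source. Any single rule applied throughout would serve. Section 13.a should say whether 8/1000 and 2/1000 are on that definition.

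Then align the forms:

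- **Post-operative form, items 4.d and 4.e:** add the instruction that matches the rule.
- **BDI form:** add the same instruction at item 5, and a leak-source field for Type A leaks recognised after surgery.
- **Intra-operative surgeon form:** add cystic duct as a named leak source at item 6, and the definition of BDI at item 11.

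The cost is a sentence or two in section 13 as well as in section 5.b, minor edits to three forms and the matching REDCap fields. Under the Types B to E example the reported BDI count would be lower, by an amount the documents do not allow one to estimate.
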